### 3.6 Measures of compliance and adherence

#### **Medications permitted**

All anti-cancer therapies (including complementary treatments/therapies) are permitted. Chemotherapy is allowed providing it is administered 4 weeks after the completion of radiotherapy.

Data on concomitant medication

All details of any anti-cancer treatments or therapies received (except complementary medications) are to be recorded on the Anti-Cancer Treatment CRF.

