### 3.9 Procedures for assessing safety

Acute toxicity will be determined at 4 weeks post randomisation using the RTOG Acute Radiation Morbidity Scoring Schema (Appendix 2). The late toxicity will then be assessed at every visit thereafter using the RTOG/EORTC Late Radiation Morbidity Scoring Schema (Appendix 2). See section 6 on Safety Reporting for more information.

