## 5.3 Sample Size

The aim of the trial is to demonstrate that low dose radiotherapy is as effective as conventional dose radiotherapy in terms of time to tumour progression within the irradiated

field. Therefore it is designed as a non-inferiority trial with the sample size planned to reliably exclude a minimum of 10% reduction in 2-year local progression free interval within the irradiated field in the experimental arm. The following table shows the total number of patients required with 5% significance level (one-sided) and 90% power in a 4-year accrual and 1-year follow up. The 2-year local progression free interval in the control arm was reported to be about 50%. The null hypothesis of non-inferiority will be rejected if the 10% difference specified in the table is excluded in the 95% upper confidence interval limit, calculated once the study is completed. We aim to accrual a total of 650 patients over 4 years.

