# 5.4 Analysis Plan

Analyses will be performed on an intention-to-treat basis. The standard log-rank approach will be applied for local progression-free interval and overall survival analysis. Comparisons of response and toxicity will be made by chi-squared tests or Mann-Whitney test wherever is appropriate.

No subgroup analyses are planned, although the size of node/lymphoma mass to be treated will be studied in an exploratory manner.

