# **APPENDIX 4: FOLLOW UP SCHEDULE**

Table 3 shows the visit schedule for the FoRT trial

Table 3: FoRT trial visit schedule

Visit number	Timepoint
1	Baseline
2	4 weeks post randomisation
3	12 weeks post randomisation – response assessment
4	6 months post randomisation
5	1 year post randomisation
6	18 months post randomisation
7	2 years post randomisation
8	3 years post randomisation
9	4 years post randomisation
10	5 years post randomisation

Once the five years of scheduled follow up are completed, patients will be followed up for survival annually until death.

The forms due at each visit are summarised in table 4 below.

Table 4: Forms due at each clinic visit

Form	Details	Compulsory / as required
Registration form	4 pages to be completed at visit 1 and faxed to UCL CTC	Compulsory
Randomisation form	1 page to be completed at visit 1 and faxed to UCL CTC	Compulsory
4-week follow up form	1 page to be posted to UCL CTC within 8 weeks of visit 2	Compulsory
Acute toxicity form	1 page to be posted to UCL CTC to be completed at visit 2 as required and posted to the UCL CTC within 8 weeks of visit 2 along with 4-week follow up form	Only required if patient experienced acute toxicity from radiotherapy
12-week follow up form	4 pages to be posted to UCL CTC within 8 weeks of visit 3	Compulsory
Follow up form	1 page to be completed at visits 4 – 10 and posted to UCL CTC within 8 weeks of visit	Compulsory up to the point of local progression
Late toxicity form	1 page to be completed at visit 3 – 10 as required and posted to UCL CTC within 8 weeks of the relevant visit along with the follow up form	Only required if patient experienced late toxicity from radiotherapy
Disease progression form	1 page to be completed at first progression within the irradiated field	Only required at local progression
Disease progression follow up form	1 page to be completed at all scheduled visits after local progression instead of the follow up form	Compulsory after local progression
Anti-cancer treatment form	1 page to be completed at visits 2-10 as required and posted to UCL CTC within 8 weeks of the relevant visit along with the follow up form	Only required if patient received cancer treatment other than their trial radiotherapy
Hospital admission form	1 page to be completed at visits 2-10 as required and posted to UCL CTC within 8 weeks of the relevant visit along with the follow up form	Only required if patient is admitted to hospital

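### Section 5.4 compares late toxicity with tests that ignore observation time, so before all patients reach 5 years a simple proportion understates the 5-year rate in both arms

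*Protocol*

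**What the plan says.** Section 5.4 of the protocol divides the outcomes by method. For two of them, "The standard log-rank approach will be applied for local progression-free interval and overall survival analysis". For the rest, "Comparisons of response and toxicity will be made by chi-squared tests or Mann-Whitney test wherever is appropriate".

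Response and acute toxicity are each read at one visit (week 12 and week 4, section 5.2). Late toxicity is different. Section 3.9 says "The late toxicity will then be assessed at every visit thereafter", and the Duration paragraph of section 1.2 carries those reviews to 5 years after randomisation. In Appendix 4, Table 4, the late toxicity form covers visits 3 to 10, that is, 12 weeks to 5 years.

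The sample size in section 5.3 assumes "5% significance level (one-sided) and 90% power in a 4-year accrual and 1-year follow up". Section 5.5 adds formal interim analyses at least once a year.

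Table 4 also fixes the paperwork. The follow up form is "Compulsory up to the point of local progression", after which a disease progression follow up form takes its place at every scheduled visit. The late toxicity form is to be "posted to UCL CTC within 8 weeks of the relevant visit along with the follow up form".

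**The concern.** A chi-squared test on the proportion with late toxicity, or a Mann-Whitney test on grades, counts a patient seen for one year the same as a patient seen for five. For an outcome that builds up over years, the resulting figure depends on how long patients have been watched as well as on the treatment.

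Two consequences have to be kept apart. The first is understatement. While follow-up is incomplete, the reported late toxicity rate falls short of the 5-year rate in both arms. The second is a possible bias between arms. If late toxicity stopped being recorded at local progression, time at risk would depend on the primary outcome, and the arm that progressed sooner would appear less toxic. If recording continues, a different issue arises. Section 3.6 says "All anti-cancer therapies (including complementary treatments/therapies) are permitted", so toxicity from later treatment of the same field can be mixed with that of the allocated dose.

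Late toxicity is one of the outcomes that a reader will set against any loss of local control in a non-inferiority comparison of a lower dose, so its rate and its comparison should be readable without knowing the follow-up pattern.

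**Working it through.** **The design's follow-up pattern.** The protocol states no figure for late toxicity, so the check starts from Table 2 to confirm that 4+1 years is what the sizing uses. For the row 50% v 40% (HR 1.32, one-sided 5%, 90% power):

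- Events = 4 × (1.6449 + 1.2816)² / (ln 1.32)² = 444.4, so 445. Table 2 states 446.
- With exponential times, uniform accrual over 4 years and 1 further year, the event probabilities are 0.6174 (control) and 0.7101 (experimental), mean 0.6638. Patients = 446 / 0.6638 = 672. Table 2 states 671.

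The row reproduces to within one event and one patient. At that date follow-up runs from 1 to 5 years, uniformly.

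**Step 1: understatement from unequal follow-up.** The late toxicity hazard is not in the documents. Assume h = 0.05 per year, constant and equal in both arms.

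- 5-year risk = 1 − exp(−5h) = 1 − exp(−0.25) = 22.1%.
- Simple proportion with follow-up uniform on 1 to 5 years = 1 − [exp(−h) − exp(−5h)] / (4h) = 1 − (0.9512 − 0.7788) / 0.20 = 13.8%.

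The simple proportion is 62% of the 5-year risk. Over a range of assumed 5-year risks:

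| Assumed 5-year risk | Simple proportion, 1 to 5 years' follow-up | Share of 5-year risk |
|---|---|---|
| 5% | 3.0% | 60% |
| 10% | 6.1% | 61% |
| 20% | 12.4% | 62% |
| 30% | 19.0% | 63% |

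The follow-up pattern is the same in both randomised arms. With equal hazards the proportions are therefore equal and the chi-squared test keeps its 5% size.

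**Step 2: what would happen if recording lapsed at local progression.** This is conditional. Inputs: section 5.3 gives the control rate ("The 2-year local progression free interval in the control arm was reported to be about 50"%), and Table 2 gives 40% in the experimental arm at the margin. Local progression hazard l = −ln(S₂)/2, which is 0.3466 (control) and 0.4581 (experimental).

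Full 5 years for everyone: observed proportion = h/(h+l) × [1 − exp(−5(h+l))].

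- 24Gy: 0.1261 × 0.8623 = 10.9%.
- 4Gy: 0.0984 × 0.9212 = 9.1%.
- Ratio 0.83, with no true difference.

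Follow-up of 1 to 5 years: replace the bracket by 1 − [exp(−L) − exp(−5L)] / (4L), with L = h + l.

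- 24Gy: 0.1261 × 0.6628 = 8.4%.
- 4Gy: 0.0984 × 0.7428 = 7.3%.
- Ratio 0.87.

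For assumed 5-year risks from 5% to 30%, the ratio is 0.83 to 0.84 with full follow-up and 0.87 to 0.88 with 1 to 5 years. With 325 patients per arm (half of 650), a two-sided 5% chi-squared test would reject in 6.5% to 14.7% and 5.6% to 9.0% of trials respectively. With equal progression in the two arms the ratio is 1.00.

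**Step 3: which remedy works.** A cumulative incidence of late toxicity that treats local progression as a competing event has, at 5 years, exactly the first formula in step 2. It would return 10.9% v 9.1% again. The cause-specific hazard ratio is h/h = 1 in the same setting. Local progression should therefore not be the competing event.

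**The case against.** The strongest reply is that late toxicity recording does not stop at local progression, and the text largely bears this out. Section 3.9 and the Duration paragraph of section 1.2 make no exception for progression. Section 6 requires all adverse events to be recorded from consent to the end of the trial. Table 4 runs the late toxicity form through visit 10, and scheduled visits continue after progression with their own compulsory form. The pairing with the follow up form is a posting instruction, and Table 4 uses the same words for the anti-cancer treatment form. Section 3.8 plainly expects later lymphoma treatment to be reported. A reader might infer from Table 4 that the sooner-progressing arm will look less toxic. The documents do not support that inference. What stands is an ambiguity: after progression, Table 4 names no form for the late toxicity form to travel with. Because the form is needed only when toxicity occurred, a missing form would look like no toxicity.

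Second, 1 to 5 years of follow-up is a sizing assumption. Section 5.3 places the primary calculation at study completion, and section 3.12 closes the trial 5 years after the last recruit. At closure every surviving patient still in follow-up has 5 scheduled years, so staggered entry no longer causes understatement. This stands, and it confines step 1 to earlier analyses: the 4+1-year date and the annual interims. Loss to follow-up remains at any date.

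Third, the phrase about appropriateness in section 5.4, or an analysis plan that is not shown, might allow another method. The natural reading, however, is a choice between the two named tests, with log-rank kept for two other outcomes. The protocol states a method here rather than leaving it open. It does not say how repeated grades are summarised, so the simple proportion used above is an assumed summary.

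Fourth, sections 1.5 and 1.6 justify the trial by efficient use of radiotherapy, so lower toxicity should not be called its main purpose. That is right.

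**Conclusion.** The point holds in a limited form. Section 5.4 names tests for late toxicity that ignore observation time, and they suit only the single-visit outcomes. At any analysis before all patients reach 5 years, a simple proportion reports about 60% to 63% of the 5-year late toxicity rate under uniform 1 to 5 years' follow-up. This assumes a constant toxicity hazard and a 5-year risk of 5% to 30%, neither given in the documents. The shortfall is the same in both arms and does not invalidate the comparison.

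A between-arm ratio of about 0.83 to 0.88 needs three further conditions: recording lapses at local progression, 4Gy is worse by the whole 10-point margin, and the true toxicity hazards are equal. The protocol points against the first, so this is a risk from loose form wording and not an established bias. Late toxicity is a secondary outcome; sample size and the primary test are unaffected.

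**What to change.** 1. In section 5.4, keep chi-squared or Mann-Whitney for response and week-4 acute toxicity. Compare late toxicity as time from randomisation to first late toxicity of a pre-specified grade (for example grade 2 or worse), with a cause-specific hazard ratio and 95% confidence interval, stratified by histology and treatment intent. Show cumulative incidence curves with death, not local progression, as the competing event. Add a sensitivity analysis censored at re-treatment of the irradiated field.
2. In Table 4, state that after local progression the late toxicity form accompanies the disease progression follow up form.

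The cost is a short text change in section 5.4, one sentence in Table 4 and a little extra analysis. The scheduled visits already supply the timing. For the sensitivity analysis, confirm that the anti-cancer treatment form shows whether later treatment covered the trial field.

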# 5.5 Interim Monitoring and Analyses

Formal interim analyses of the accumulating data will be performed at regular intervals (at least annually) for review by an Independent Data Monitoring Committee (IDMC) (see also section 9.3). The IDMC will be asked to give advice on whether the accumulated data from the trial, together with results from other relevant trials, justifies continuing recruitment of further patients or further follow up. A decision to discontinue recruitment, in all patients or in selected subgroups will be made only if the result is likely to convince a broad range of clinicians including participants in the trial and the general clinical community. If a decision is made to continue, the IDMC will advise on the frequency of future reviews of the data on the basis of

accrual and event rates. The IDMC will make recommendations to the Trial Steering Committee (TSC, see section 9.2) as to the continuation of the trial.

# 6. SAFETY REPORTING

#### **Definitions of Adverse Events**

The following definitions have been adapted from Directive 2001/20/EC and ICH GCP E6:

### Adverse Event (AE)

Any untoward medical occurrence or effect in a patient treated on a trial protocol, which does not necessarily have a causal relationship with this treatment. An AE can therefore be any unfavourable and unintended sign (including an abnormal laboratory finding), symptom or disease temporally associated with the use of the trial treatment, whether or not related to the trial treatment.

#### **Adverse Reaction**

All untoward and unintended responses to a trial treatment related to any dose administered. A causal relationship between the trial treatment and an adverse event is at least a reasonable possibility, i.e. the relationship cannot be ruled out.

### Serious Adverse Event (SAE) or Serious Adverse Reaction:

An adverse event or adverse reaction that at any dose:

- Results in death
- Is life threatening (The term "life-threatening" refers to an event in which the subject was at risk of death at the time of the event. It does not refer to an event that hypothetically might have caused death if it were more severe.)
- · Requires in-patient hospitalisation or prolongs existing hospitalisation
- Results in persistent or significant disability/incapacity
- Is a congenital anomaly or birth defect
- Is otherwise medically significant (i.e. withdrawal reactions, all accidental or intentional overdoses whether they result in an adverse event or not, or any event which the investigator considers significant but which is not covered by the above.)

### Suspected Unexpected Serious Adverse Reaction (SUSAR)

A serious adverse reaction, the nature or severity of which **is not consistent** with the applicable trial treatment information.

A serious event or reaction is not defined as a SUSAR when:

- · it is serious but expected
- it does not fit the definition of an SAE, whether expected or not

## **Reporting Procedures**

### **All Adverse Events (AEs)**

All adverse events that occur between informed consent and the end of the trial must be recorded in the patient notes and the trial CRFs. Information regarding dates of event onset and resolution, outcome, severity and causality for the trial treatment must be recorded. Those meeting the definition of a Serious Adverse Event (SAE) must also be reported to the UCL CTC using the trial specific SAE Report (see Serious Adverse Events section for details).

Pre-existing conditions do not qualify as adverse events unless they worsen.

#### **Adverse Event Term**

An adverse event term needs to be provided for each adverse event, preferably using the Short Name as listed in the Common Terminology Criteria for Adverse Events v3.0 (CTCAE), available online at: http://ctep.cancer.gov/protocolDevelopment/electronic\_applications/docs/ctcaev3.pdf.

#### Severity

Severity for each adverse event must be determined by using the RTOG Radiation Morbidity Scoring Criteria (Appendix 2), wherever possible. If the adverse event is not covered by the RTOG criteria, the Common Terminology Criteria for Adverse Events v3.0 (CTCAE) can be used. The criteria are available online at:

http://ctep.cancer.gov/protocolDevelopment/electronic\_applications/docs/ctcaev3.pdf.

In those cases where neither the RTOG nor the CTCAE criteria do not apply, severity should be coded according to the following criteria:

- 1 = Mild
- 2 = Moderate
- 3 = Severe
- 4 = Life threatening
- 5 = Fatal

### Serious Adverse Events (SAEs)

All SAEs that occur between informed consent and 30 days post the last trial treatment administration (or after this date if the site investigator feels the event is related to the trial treatment) must be submitted to the UCL CTC by fax within 1 business day of observing or learning of the event, using the trial specific SAE Report. All sections on the SAE Report must be completed.

### Causality

Site investigators must perform an evaluation of causality for each SAE. Causal relationship to the trial treatment must be determined as follows:

#### None

There is no evidence of any causal relationship.

### Unlikely

There is little evidence to suggest a causal relationship (e.g. because the event did not occur within a reasonable time after administration of the trial treatment). There is another reasonable explanation of the event (e.g. the patient's clinical condition, other concomitant medications).

#### Possible

There is some evidence to suggest a causal relationship (e.g. because the event occurs within a reasonable time after administration of the trial treatment). However, the influence of other factors may have contributed to the event (e.g. the patient's clinical condition, other concomitant medications).

#### Probable

There is evidence to suggest a causal relationship and the influence of other factors is unlikely.

#### Definitely

There is clear evidence to suggest a causal relationship and other possible contributing factors can be ruled out.

#### **Expectedness**

Site investigators must perform an evaluation of expectedness for all SAEs regardless of causal relationship to the trial treatment. This evaluation must be performed using the list of expected adverse events in appendix 2 of the protocol. Expectedness of the event for the trial treatment must be determined as follows:

#### Expected

The event is listed as an expected adverse event in the protocol appendix.

### Unexpected

The event is not listed as an expected adverse event in the protocol appendix or, the severity of the event is greater than that listed in the protocol appendix for example:

- the event is life threatening or fatal (unless stated in the protocol appendix as expected).
- the patient presents with an event which is considered to be moderate or severe,
   but only mild is listed as expected in the protocol appendix.

### **Events which do not Require Reporting as an SAE**

The following events do not require reporting as an SAE, but must be recorded in the relevant section(s) of the CRF:

- disease progression
- disease related deaths
- admissions for palliative care

All SAEs must be reported by faxing a completed SAE Report within 1 business day of becoming aware of the event to the UCL CTC [contact]

26

# **Adverse Event Reporting Flowchart Adverse Event Complete CRF Assign Severity Grade** CRF to be submitted at the time point stated in the protocol Does the event meet the definition of Serious Adverse **Event (SAE) NOT SERIOUS SERIOUS** Criteria: Results in death Is life threatening Results in persistent or significant disability/incapacity Requires in-patient hospitalisation or prolongs existing hospitalisation Results in a congenital anomaly or birth defect Is otherwise medically significant Disease Not disease related related **Event listed in Event NOT listed in** protocol as not protocol as not requiring reporting requiring reporting as SAE as SAE No action **Complete SAE report** Investigator to assess expectedness Is the event listed as an expected adverse event for the trial treatment in the trial protocol appendix? Fax report to the UCL CTC within 1 business day

Cancer Research UK - FoRT Trial

**SAE Follow-Up Reports** 

All SAEs must be followed-up until resolution. Site investigators must provide follow-up SAE

Reports if the SAE had not resolved at the time the initial report was submitted.

On receipt of the SAE Report, the UCL CTC will evaluate the event for seriousness and

expectedness to determine whether or not the case qualifies for expedited reporting. If this is

difficult to determine, the Chief Investigator and/or Trial Management Group will be consulted

for their opinion. In the case of discrepant views, both opinions will be reported.

**SUSARs** 

If the event is evaluated, by either the site or the UCL CTC, as a related and unexpected SAE,

the UCL CTC will submit a report to MREC within 15 calendar days.

The UCL CTC will inform all Principal Investigators of any SUSARs which occur on the trial. Site

investigators will receive expedited SUSAR reports that must be processed according to local

requirements.

Additional Safety Monitoring at the UCL CTC

The UCL CTC will also monitor safety data for any trial related events that are not considered

related to the trial treatment. In the event that any trial procedures appear to be resulting in

adverse events, the Chief Investigator and/or Trial Management Group will be contacted for their

opinion. If it is declared necessary to review the conduct of the trial, the UCL CTC will inform

MREC, as appropriate.

**Pregnancy** 

If a female patient or a female partner of a male patient becomes pregnant at any point during

the trial, a completed trial specific Pregnancy Report must be submitted to the UCL CTC by fax

within **1 business day** of learning of its occurrence.

All pregnancies must be reported by faxing a completed Pregnancy

Report within 1 business day of becoming aware of the event to the

